**Criteria 3**

**ALT  $\geq$ 3X ULN + Bilirubin  $\geq$ 2X ULN (>35% direct)**

or

**ALT  $\geq$ 3X ULN + INR >1.5:**

Note: INR testing is not required per protocol and the threshold value does not apply to subjects receiving anticoagulants.

- Subject must not receive any further injections of RBP-6000.
- Contact the Indivior Medical Monitor within 24 hours of learning of the abnormality to discuss subject safety and any addition laboratory testing required.
- Make every reasonable attempt to have the subject return to the clinic within 24 hours for repeat liver chemistries, additional testing and close monitoring (with specialist or hepatology consultation recommended).
- Monitor the subject twice weekly until liver chemistries (ALT, AST, alkaline phosphatase, bilirubin) resolve, stabilize or return to within baseline values.
- Upon completion of the safety follow-up, the subject must be withdrawn from the study unless further follow-up is required.

3.0 LIST OF ABBREVIATIONS

AE	Adverse Event
ALP	Alkaline Phosphatase
ALT	Alanine Aminotransferase
AST	Aspartate Aminotransferase
BMI	Body Mass Index
CDF	Cumulative Distribution Function
CNS	Central nervous system
CRF	Case Report Form
CTMS	Clinical Trials Management System
C-SSRS	Columbia Suicide Severity Rating Scale
ECG	Electrocardiogram
EOS	End of Study
ET	Early Termination
GGT	Gamma-glutamyl Transpeptidase
HDL-C	High-density lipoprotein - Cholesterol
IA	Interim Analysis
ICF	Informed Consent Form
IDC	Individual Drug Counseling
LDH	Lactate dehydrogenase
MedDRA	Medical Dictionary for Regulatory Activities
OTC	Over The Counter
PDV	Protocol Deviation
PT	Preferred Term
OUD	Opioid Use Disorder
SAP	Statistical Analysis Plan
SAE	Serious Adverse Event
SC	Subcutaneous
SD	Standard Deviation
SDTM	Study Data Tabulation Model
SDTMIG	Study Data Tabulation Model Implementation Guide
SI	International System
SOC	System Organ Class
SUSAR	Suspected Unexpected Serious Adverse Event
TBIL	Total Bilirubin
TEAE	Treatment-Emergent Adverse Event
TFLs	Tables, Listings, and Figures
UDS	Urine Drug Screen

ULN	Upper Limit of Normal
VAS	Visual Analog Scale
WHODRUG	World Health Organization Drug Dictionary

4.0 INTRODUCTION

This statistical analysis plan (SAP) describes the statistical methods to be used during the final reporting and analyses of data collected for the full study (Protocol INDV-6000-301).

This SAP should be read in conjunction with the study protocol and case report form (CRF). This version of the plan has been developed using the protocol dated 30SEP2016 and CRF dated 17Mar2017.

This is a multicenter, open-label, RBP-6000 treatment extension study in which approximately 300 subjects diagnosed with moderate to severe Opioid Use Disorder (OUD) will be enrolled. Enrollment is defined as the first dose of RBP-6000 administered for this study. Only subjects who have completed the End of Study (EOS) procedures for Study RB-US-13-0003, have signed the INDV-6000-301 informed consent form (ICF), and meet all enrollment criteria will be considered for inclusion in this study.

The Institutional Review Board (IRB) approved ICF may be shared with the potential subject up to 2 months before the EOS Visit for Study RB-US-13-0003 to discuss this study as a possible treatment option. However, the ICF for Study INDV-6000-301 must not be signed until all assessments for the RB-US-13-0003 EOS Visit are complete.

The RB-US-13-0003 EOS assessments completed at the EOS Visit will serve as part of the screening assessments for this study. In addition, medical history will be collected, height measured, and subjects will be requested to complete a Columbia Suicide Severity Rating Scale (C-SSRS) baseline survey.

On Day 1 (the date of the first injection), eligible subjects will receive a subcutaneous (SC) injection of RBP-6000. For each injection, subjects may receive either 100 mg or 300 mg of RBP-6000 (to be referred to as 100/300 Flex for the remainder of this document), based on the medical judgment of the investigator. Following RBP-6000 injection, vital signs and the injection site will be assessed. The injection site will be assessed by the site for pain, tenderness, erythema/redness, induration and swelling using a 5-point severity scale (the Injection Site Grading Scale). In addition, the subject will assess their own injection site pain using a visual analog scale (VAS) (referred to as the Injection Site Pain VAS). Before departing the site, the subject will also be assessed for adverse events (AEs) and use of concomitant medications.

Subjects will not be permitted to receive supplemental buprenorphine during the RBP-6000 treatment period (Day 1 to EOS/ET Visit). Subjects who require supplemental buprenorphine pharmacotherapy during the RBP-6000 treatment period will be withdrawn from the study and referred for appropriate treatment.

Subjects will return to the site for monthly injection visits every 28 days (-2 / +7 days) for a total of up to 6 injections. Subjects are not required to complete all 6 injections and may choose to “early terminate” (ET) the study at any time.

At each subsequent visit (Injection Visits 2 through 6) the following procedures and assessments will be performed: urine pregnancy test for all female subjects who are of childbearing potential before each injection; evaluation of previous injection site for potential reaction and evidence of attempts to remove the depot; collection of vital signs pre- and post-injection; RBP-6000 injection; urine drug screen (UDS); C-SSRS since last visit, counseling (manual-guided behavioral therapy); local injection site grading; subject self-assessment of injection site pain (Injection Site Pain VAS); use of concomitant medications; and assessment for AEs. Laboratory tests (hematology, chemistry and urinalysis) may be requested by the investigator on an ad-hoc basis as necessary to further examine any AEs.

Alternative treatment options should be assessed at least two months before EOS at each visit, however it is recommended where possible to assess at every visit.

At the EOS/ET Visit, the following procedures and assessments will be performed: urine pregnancy test for all female subjects who are of childbearing potential; evaluation of previous injection site for potential reaction and evidence of attempts to remove the depot; vital sign measurements; UDS; C-SSRS since last visit, counseling (manual-guided behavioral therapy); use of concomitant medications; assessment for AEs; brief physical exam; body weight measurement (to determine a subject's body mass index [BMI]); hip and waist circumference measurement (to determine a subject's hip-to-waist ratio); and laboratory tests (hematology, chemistry, urinalysis).

Approximately 4 weeks after EOS/ET Visit, all subjects should be contacted by telephone or face-to-face visit safety follow-up assessment of AEs and use of any concomitant medications.

5.0 **OBJECTIVE**

Indivior is developing RBP-6000, a long-acting formulation of buprenorphine for monthly subcutaneous (SC) injection, for the treatment of Opioid Use Disorder (OUD).

The objective is to provide ongoing treatment with RBP-6000 and safety monitoring for subjects who complete the RB-US-13-0003 study and for whom a new treatment venue has not been identified or arranged.

6.0 SUBJECT POPULATIONS AND TREATMENT GROUPS

6.1 SCREENED POPULATION

The Screened Population Set includes any subject who signed the informed consent form.

6.2 SAFETY ANALYSIS SET

The Safety Analysis Set consists of all subjects who received at least one dose of RBP-6000.

6.3 TREATMENT GROUPS

There is only one treatment group in the trial and all subjects will be labeled with “RBP-6000 (100/300 mg Flex)”.

7.0 SUBJECT DISPOSITION

The number and percentage of subjects screened and screen failures, if any, will be summarized.

The number and percentage of subjects who entered the RBP-6000 treatment period (i.e., Treatment Period, and see definition in Section 20.1), and who completed the study will be presented, together with the number and percentage of subjects who prematurely discontinued from the RBP-6000 treatment period along with reasons for study discontinuation will be summarized.

In summary, it is that the following number and percentage of subjects will be presented:

- All subjects who were considered screen-failures
- All subjects who entered the RBP-6000 treatment period (i.e., Treatment Period, and see definition in Section 20.1)
 - All subjects who completed the study
 - All subjects who prematurely discontinued from the RBP-6000 treatment period along with reasons for study discontinuation.

The number and percentage of subjects included in each analysis set will be presented.

A listing of the inclusion/exclusion reasons for screen failures will be provided, if any.

8.0 PROTOCOL DEVIATIONS

A listing of important protocol deviations (PDV) will be presented by subject using the Safety Analysis Set. An important deviation is defined as:

- Subject was deemed eligible for the study but did not meet inclusion/exclusion criteria
- Consent was not obtained from the subject

9.0 DEMOGRAPHICS AND OTHER BASELINE CHARACTERISTICS

Demographic and baseline characteristics (sex, ethnicity, race, age [years and categories of ≥ 18 - <30 , ≥ 30 - <45 , ≥ 45 - <60 , ≥ 60 and ≥ 65], weight [kg], height[cm], waist[cm], hip[cm], waist-to-hip ratio and body mass index [BMI; kg/m²]) will be summarized using descriptive statistics for subjects in the Safety Analysis Set. Qualitative variables (sex, ethnicity, race, age categories, BMI categories) will be summarized using frequencies while quantitative variables (age, weight, height, BMI, waist, hip and waist-to-hip ratio) will be summarized using mean, SD, median, minimum, and maximum. Demographic and baseline data will also be listed for all subjects.

9.1 SUBSTANCE USE HISTORY

Substance use history will be presented by substance and previous use for subjects in the Safety Analysis Set. Tobacco use [never, former, current], caffeine use [never, former, current], alcohol use [never, former, current]) will be summarized using descriptive statistics for subjects in the Safety Analysis Set. Qualitative variables (tobacco use, caffeine use, alcohol use) will be summarized using frequencies.

9.2 MEDICAL HISTORY

Medical history will be coded using Medical Dictionary for Regulatory Activities (MedDRA) version 19.0 and summarized by the number and percentage of subjects in each System Organ Class (SOC), Preferred Term (PT) and in the Safety Analysis Set. Subjects will be counted only once for each PT, only once at the System Organ Class (SOC), and only once at subject level for the counting of total number of subjects with a medical history term. Counts will be presented in descending frequency unless otherwise specified.

Listings of medical history events for each subject will be provided.

9.3 PRIOR AND CONCOMITANT MEDICATIONS

Prior and concomitant medications will be categorized by preferred name and drug category class (CMCLAS, ATC level 4 class per World Health Organization Drug Dictionary [WHODRUG]); and will be summarized for the Safety Analysis Set. The number and percentage of subjects using each medication will be displayed together with the number and percentage of subjects using at least one medication.

Prior medications rolling over from prior studies will be considered for both prior and concomitant medications in this study.

Prior Medications

For a subject in the Safety Analysis Set, prior medications will include any medication taken within 28 days prior to subject's first dose of RBP-6000 in the INDV-6000-301 study.

Concomitant Medications

Concomitant medications are defined as prescribed medications and Over The Counter (OTC) preparations, including herbal preparations and vitamins, other than RBP-6000.

All prior medications will be presented in separate listing for the Safety Analysis Set.

A summary of all concomitant medications taken from Day 1 to last dose + 28 days will be presented as during RBP-6000 dosing for the Safety Analysis Set.

A summary of all concomitant medications taken from the last dose + 29 days to the last recorded assessment will be presented as post RBP-6000 dosing for the Safety Analysis Set.

A listing of all subject's concomitant medications during RBP-6000 dosing and post RBP-6000 dosing will be listed separately.

After imputing the incomplete start/end date of non-study medications (as described in Section 20.8), the determination of concomitant medication during vs. post RBP-6000 dosing follows the rules in the [Table 1](#) below.

Table 1: Determination of Concomitant Medication during vs. Post RBP-6000 dosing

		Start date of Non-Study Medication			
		missing	Prior to day 1	from Day 1 to last dose +28 days (inclusive)	Post last dose+28 days
End date of non-study medication	missing	During ¹ , Post ²	During, Post	During, Post	Post
	from Day 1 to last dose +28 days (inclusive)	During	During	During	Data error
	Post last dose+28 days	During, post	During, post	During, post	post

¹ during RBP-6000 dosing. ² post RBP-6000 dosing

CNS Depressants

If a subject satisfies any of the three criteria below, then the subject is classified as taking a CNS Depressant

Criterion 1:

[INDV-6000-301] SAP Version 1.0

October 6, 2017

Subject with concomitant medication and its class (CMCLAS) in ('BENZODIAZEPINE RELATED DRUGS' 'BENZODIAZEPINE DERIVATIVES' 'DIAZEPINES, OXAZEPINES, THIAZEPINES AND OXEPINES' 'OTHER HYPNOTICS AND SEDATIVES' 'PHENOBARBITAL'). Defined in the later section (CNS Depressant Medication Categories)

Criterion 2:

Subject with substances 'Barbiturates' or 'Benzodiazepine' detected positive in Urine Drug Screen during the Treatment Period.

CNS Depressant Medication Categories

Benzodiazepine-related drugs

If the Concomitant medication class is "BENZODIAZEPINE RELATED DRUGS" or detection of substances "Benzodiazepine" positive in Urine Drug Screen positive during the Treatment Period, then it is derived as Benzodiazepine related drugs.

Benzodiazepine derivatives

If the Concomitant medication class contains ("BENZODIAZEPINE DERIVATIVES", "DIAZEPINES, OXAZEPINES, THIAZEPINES AND OXEPINES") during the Treatment Period then it is derived as Benzodiazepine Derivatives.

Other Hypnotics and Sedatives

If the Concomitant medication class is ("OTHER HYPNOTICS AND SEDATIVES") during the Treatment Period, then it is derived as Other Hypnotics and Sedatives.

Phenobarbital and Derivatives

If the Concomitant medication class is "PHENOBARBITAL" during RBP-600 dosing or detection of substances Barbiturates positive in Urine Drug Screen during the Treatment Period, then it is derived as Phenobarbital and Derivatives.

Summary of subjects who have taken CNS depressant medications during RBP-6000 dosing (from Day 1 to last dose + 28 days) be provided. CNS depressant medications can be indemnified from two sources in this study: Concomitant medications or Urine Drug Screen as in the table below ([Table 2](#)).

Table 2: Summary of Subjects Who Have Taken CNS Depressant Medications During RBP-6000 Dosing

Any CNS depressant (from Concomitant medications) taken with a start date after Day 1 to last dose + 28 days
Benzodiazepine-related Drugs Benzodiazepines Derivatives Other Hypnotics and Sedatives Phenobarbital and Derivatives
Any positive CNS depressant (from UDS) during the treatment period
Barbiturate Positive Benzodiazepines Positive

Preferred terms at drug class ATC level 3 of drug categories Benzodiazepine-related Drugs, Benzodiazepines Derivatives, Other Hypnotics and Sedatives and Phenobarbital and Derivatives will be summarized in the safety analysis set (see Appendix 1 for the list of CNS depressant medications).

A separate table for CNS depressant medications will be summarized for post RBP-6000 dosing

CYP3A4 Inhibitor Medication Categories

The following four categories (Unclassified, Weak, Moderate and Strong) are used from Appendix 2 containing Generic/Brand name of the CYP3A4 Inhibitor medication and its categories.

Preferred terms at drug class ATC level 3 of CYP3A4 Inhibitor Medications (Unclassified, Weak, Moderate or Strong inhibitors) during RBP-6000 dosing and post RBP-6000 dosing will be summarized in separate tables.

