### **6.10.1 Prohibited Concomitant Medications**

The sponsor must approve any prohibited concomitant medications before administration except in cases of immediate medical need. In cases of immediate medical need, consult the Medical Monitor as soon as possible following administration of a prohibited medication for any further questions and to ensure appropriate documentation. All concomitant medications should be recorded in the eCRF.

The following medications are prohibited:

- All cytochrome P450 3A4 and 2C8 inducers and inhibitors inclusive of, but not limited to those in [Appendix 3](#)
- Buprenorphine (in addition to RBP-6000 treatment)
- OTC and/or herbal supplements with the potential to prolong QTc. (For example: famotidine (e.g., Pepcid brand), ephedrine, and some Chinese herbal supplements.)

The use of all opioids should be avoided in this study.

- If the subject self-medicates with these medications, document reason for use appropriately.
- Any prescribed opioids for other uses (such as pain) should be discussed with the Medical Monitor.

The use of the following medications requires careful consideration, and should be discussed with the Medical Monitor. If treatment is necessary, careful monitoring is required for:

- prescription medications known to prolong the QTc interval
- general anesthetics, benzodiazepines, phenothiazines, other tranquilizers, and sedative/hypnotics.

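### SAP 9.3 derives positive urine screens into two CNS-depressant categories that its Table 2 reports as concomitant medications, so the section contradicts itself on data source

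*SAP*

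**What the plan says.** SAP 9.3, under CNS Depressant Medication Categories, gives one rule for each of four categories.

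- *Benzodiazepine-related drugs*: a matching medication class or a positive screen. The rule ends "positive in Urine Drug Screen positive during the Treatment Period, then it is derived as Benzodiazepine related drugs".
- *Phenobarbital and derivatives*: a matching medication class or "detection of substances Barbiturates positive in Urine Drug Screen during the Treatment Period, then it is derived as Phenobarbital and Derivatives".
- *Benzodiazepine derivatives*: medication class only. The rule ends "during the Treatment Period then it is derived as Benzodiazepine Derivatives" and names no urine result.
- *Other hypnotics and sedatives*: medication class only.

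Table 2 of the same section then sets out the summary in two blocks. The medication block is headed "Any CNS depressant (from Concomitant medications) taken with a start date after Day 1 to last dose + 28 days" and has the four category names as its rows. The urine block is headed "Any positive CNS depressant (from UDS) during the treatment period" and has its own rows for barbiturate and benzodiazepine positives.

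Earlier in SAP 9.3, concomitant medications are defined as prescribed and over-the-counter preparations. A urine result is not part of that definition. The output concerned is Table 14.1.5.4, whose title says that it draws on both medication data and urine screening.

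**The concern.** Using both sources in one table is intended and reasonable. The difficulty is that the category rules and the table layout disagree about which source fills two of the rows. The rules are the only place where those rows are defined, and they admit urine results. The heading above the rows excludes them.

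What is at stake is how the table can be read. Safety monitoring is part of the study's single objective, and SAP 12.1.8 and 12.1.9 make CNS depression and respiratory depression topics of special interest. A reader looking for background co-use of depressants would take the medication block as reported medication and the urine block as what the screens found. Under the category rules, two rows of the medication block hold a mixture, and nothing in the label shows it.

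**Working it through.** The plan states no figure on this point, so there is none to reproduce. The check applies the SAP 9.3 rules literally to subject profiles, with and without the UDS clauses, and compares the results with the Table 2 headings.

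**Step 1. Where each profile is counted.**

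| Subject | Medication rows, rules as written | Medication rows, medication records only | UDS rows (same either way) |
|---|---|---|---|
| Benzodiazepine-positive, no CNS depressant recorded | Benzodiazepine-related | none | Benzodiazepines Positive |
| Barbiturate-positive, no CNS depressant recorded | Phenobarbital and Derivatives | none | Barbiturate Positive |
| Benzodiazepine derivative recorded, benzodiazepine-positive | Benzodiazepine-related and Derivatives | Derivatives | Benzodiazepines Positive |
| Other hypnotic recorded, benzodiazepine-positive | Benzodiazepine-related and Other Hypnotics | Other Hypnotics | Benzodiazepines Positive |
| Benzodiazepine derivative recorded, no positive screen | Derivatives | Derivatives | none |
| Phenobarbital-class medication recorded, barbiturate-positive | Phenobarbital and Derivatives | Phenobarbital and Derivatives | Barbiturate Positive |

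The first four profiles differ between the two readings and the last two do not. The third profile can occur: protocol 6.10 allows subjects with prescribed benzodiazepines to be considered case by case. The *Benzodiazepine Derivatives* row, the *Other Hypnotics and Sedatives* row and the UDS block are the same under both readings.

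**Step 2. Effect on the header row of the medication block.** The SAP does not say how this row is built. There are two possibilities.

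- Built from medication records, as its label says: a category row beneath it can exceed it, because the category row admits urine-only subjects and the header does not.
- Built from the four categories: it is inflated. Let u be the share of subjects with a benzodiazepine-positive screen and r the share of those with a recorded CNS-depressant medication. The excess is u × (1 − r).

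**Step 3. Illustration of size.** N = 300 comes from SAP 18.0. The documents give no positivity rate, so u is an assumed range of 5% to 20%. It is also assumed that no one has a benzodiazepine-related drug recorded.

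- Benzodiazepine-related row as written, N × u: 300 × 0.05 = 15; 300 × 0.10 = 30; 300 × 0.20 = 60.
- The same row from medication records only: 0 in each case, by the assumption.
- Header row, if built from the categories, at u = 10%: 10% × (1 − 0) = 10.0 percentage points for r = 0; 10% × (1 − 0.5) = 5.0 for r = 50%; 10% × (1 − 1) = 0.0 for r = 100%.
- Header row at r = 0 for the ends of the range: 5.0 points at u = 5% and 20.0 points at u = 20%.

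The header excess therefore disappears if every positive subject also has a recorded CNS depressant. The excess in the category row does not, because a recorded derivative does not remove the subject from the benzodiazepine-related row.

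**The case against.** The strongest reply is that the table is ambiguous rather than wrong. Table 2 separates the sources by heading and gives UDS its own rows, so a programmer who works from the headings would produce correctly sourced rows. The combined categories could be meant for the overall subject-level classification, where the SAP does combine sources (Criterion 2). This shows that a correct table is possible, but it leaves the conflict in place: the category rules are the only definition of the rows, and two programmers each following the SAP could produce different counts.

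A second reply is that the impact is small, and this stands. The study has one treatment group and no subgroup analyses, and the SAP does not cross-tabulate depressant use with adverse events. Each source can also be seen separately: medications in Table 14.1.5.2 and Listing 16.2.11.1, urine results in Table 14.2.1.3 and Listing 16.2.30.

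A third reply is that the SAP does not make the categories mutually exclusive, so being in two is not itself an error. That also stands. The problem in the third profile is that one of the two entries has no medication record behind it.

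A reader might infer three stronger points, which the documents do not support.

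- *That benzodiazepine positives go to the wrong class.* This depends on which drugs the dictionary places under related drugs and which under derivatives, and the documents do not say. SAP 9.3 points to Appendix 1 for the list of CNS-depressant medications, but that appendix holds adverse-event terms. The documents show only an assignment without a stated reason.
- *That the class value PHENOBARBITAL would miss prescribed barbiturates.* The SAP describes the class variable as "drug category class (CMCLAS, ATC level 4 class per World Health Organization Drug Dictionary [WHODRUG", but no document shows the values it takes. Protocol Appendix 3, which lists phenobarbital and barbiturates, is a table of enzyme inhibitors and inducers and says nothing about medication coding.
- *That phenothiazines are wrongly left out.* Protocol 6.10.1 names "general anesthetics, benzodiazepines, phenothiazines, other tranquilizers, and sedative/hypnotics" as needing discussion with the Medical Monitor and careful monitoring. That does not define CNS depressants for analysis, and the SAP does not claim to match it.

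**Conclusion.** The point holds as a contradiction on data source within SAP 9.3, limited to two of the four categories. Following the stated definitions puts urine-only subjects into rows labelled as concomitant medications and counts them again in the UDS block. It also places a subject with a recorded benzodiazepine derivative and a positive screen in both benzodiazepine categories on one reported medication.

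The direction is certain under those definitions: the two rows can only be too large as counts of reported medication. The size is not known. The figure of 15 to 60 subjects against 0 is an illustration and rests on three assumptions: positivity of 5% to 20%, no recorded benzodiazepine-related drug, and the category rules being used to fill the rows. If the Table 2 headings were followed instead, the error would not arise.

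Only descriptive CNS-depressant output (Table 14.1.5.4) is affected. It is worth correcting because it changes reported counts and is cheap to settle.

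**What to change.** In SAP 9.3, delete the UDS clause from the definitions of *Benzodiazepine-related drugs* and *Phenobarbital and derivatives*, so that all four medication rows of Table 2 use concomitant-medication records only. Keep positive screens in the *Barbiturate Positive* and *Benzodiazepines Positive* rows, and keep UDS as Criterion 2 in the overall CNS-depressant classification, so that no urine information is lost.

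Alternatively, if combined categories are wanted, keep the clauses and relabel the two rows as drawn from both sources, outside the heading for concomitant medications.

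Either change costs a few lines of SAP text and derivation code and needs no new data. The downside of the first option is that the two medication rows become smaller.

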18.0 DETERMINATION OF SAMPLE SIZE

This study is designed to provide ongoing treatment with RBP-6000 and to assess the safety monitoring for subjects who complete the RB-US-13-0003 study and for whom a new treatment venue has not been identified or arranged. Approximately 300 subjects who completed Study RB-US-13-0003 will be enrolled into this study.

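### SAP 9.3 looks for barbiturates by testing a drug name against a class variable, and reports a broader class under the benzodiazepine-derivatives label

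*SAP*

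**What the plan says.** SAP 9.3 categorizes medications by preferred name and by "drug category class (CMCLAS, ATC level 4 class per World Health Organization Drug Dictionary [WHODRUG"]). Drug name and drug class are therefore separate variables, and CMCLAS is the class.

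The part on CNS depressants opens with "If a subject satisfies any of the three criteria below, then the subject is classified as taking a CNS Depressant" and then gives two criteria:

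- Criterion 1 requires CMCLAS to take one of five values: two benzodiazepine classes (related drugs and derivatives), then "DIAZEPINES, OXAZEPINES, THIAZEPINES AND OXEPINES' 'OTHER HYPNOTICS AND SEDATIVES' 'PHENOBARBITAL".
- Criterion 2 is a urine drug screen (UDS) positive for barbiturates or benzodiazepine in the Treatment Period.

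Four category rules follow. The benzodiazepine derivatives class and the class "DIAZEPINES, OXAZEPINES, THIAZEPINES AND OXEPINES" share one rule, which ends "during the Treatment Period then it is derived as Benzodiazepine Derivatives". The rule for the phenobarbital category requires the class to be `PHENOBARBITAL`, or a barbiturate-positive UDS. The results go to Tables 14.1.5.4 and 14.1.5.5.

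Protocol Appendix 3, in its list of CYP3A4 inducers, has phenobarbital as one entry (example brand Luminal) and barbiturates as another (Nembutal, Luminal).

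**The concern.** The filter seems to mix two kinds of value. Four of the five entries read as classes. The fifth is a drug name, and it is the only entry meant to find barbiturates. If CMCLAS holds what the SAP says it holds, a test for that name has nothing to match. The concomitant-medication part of the phenobarbital row could then be zero because of the coding rule, and a reader would take the zero as evidence that nobody used these drugs.

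The second doubt is the label. The SAP lists the diazepines class as a value distinct from benzodiazepine derivatives, then reports both under the benzodiazepine name. The class name also covers oxazepines, thiazepines and oxepines.

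The study's objective includes safety monitoring, and SAP 12.1.8 and 12.1.9 make CNS depression and respiratory depression topics of special interest. Tables 14.1.5.4 and 14.1.5.5 are where a reader will look for co-use of depressants alongside those events.

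**Working it through.** No power or error-rate calculation applies. The study is descriptive (SAP 6.3: "There is only one treatment group in the trial and all subjects will be labeled with" a single flexible-dose name), and the SAP gives no figure to reproduce here. The check compares the text of the rules.

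**Step 1: do the category rules cover Criterion 1?** Yes. Together, the four rules use exactly the five Criterion 1 values.

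| CMCLAS value | Reported category |
|---|---|
| Benzodiazepine related drugs | Benzodiazepine-related drugs |
| Benzodiazepine derivatives | Benzodiazepine derivatives |
| Diazepines, oxazepines and so on | Benzodiazepine derivatives |
| Other hypnotics and sedatives | Other hypnotics and sedatives |
| `PHENOBARBITAL` | Phenobarbital and derivatives |

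**Step 2: can the barbiturate entry match?** A search of the five values for the word barbiturate finds it in none. That leaves `PHENOBARBITAL`, and there are two possibilities:

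- CMCLAS holds only classes, as defined. The test then finds no record, not even phenobarbital itself.
- CMCLAS does contain that string for some records. The test then finds those records, but no value names the remaining barbiturates, although the row label promises derivatives too.

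Barbiturates are under-captured either way, unless the dictionary places them in one of the other four classes. In that case they would reach the any-depressant line, but in the wrong row.

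**Step 3: do the two sources of the phenobarbital category agree?** No. The UDS route accepts any barbiturate-positive result. The medication route accepts one drug name. One category is built from two definitions.

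**Step 4: does the diazepines class fit its label?** Its name extends beyond benzodiazepines, and the SAP itself keeps it apart from the benzodiazepine derivatives class. The documents do not say which drugs it holds. SAP 9.3 refers to its Appendix 1 for a list of CNS depressant medications, but that appendix contains adverse-event terms only and Appendix 2 lists CYP3A4 inhibitors, so the text cannot settle the question.

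**Step 5: size per subject.** SAP 18.0 gives the denominator: "Approximately 300 subjects who completed Study RB-US-13-0003 will be enrolled into this study". One subject missed or misfiled moves a percentage by 100 / 300 = 0.33 points. Neither document gives usage rates, so the number of such subjects is unknown.

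**The case against.** The strongest reply is that little is lost.

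- SAP 9.3 summarizes all concomitant medications by preferred name and class (Tables 14.1.5.2 and 14.1.5.3, Listings 16.2.11.1 and 16.2.11.2). Table 14.2.1.3 summarizes UDS positives by substance. Recorded barbiturates appear in the former whatever the filter does.
- Criterion 2 still brings in barbiturates detected at visits, and the SAP's layout for this summary has a barbiturate-positive row.
- Barbiturates are prohibited as CYP3A4 inducers (Protocol 6.10.1 and Appendix 3). Exclusion criterion 4 bars inducer use within 28 days of Day 1 without Medical Monitor approval. Few recorded users are to be expected.
- The values actually stored in CMCLAS, and the contents of the diazepines class, are not in the documents.

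All of this stands. It limits the impact and rules out calling any row certainly empty or inflated. It does not make the rule correct as written.

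A reader might also infer that the filter should contain every group in Protocol 6.10.1, which asks for careful consideration of "general anesthetics, benzodiazepines, phenothiazines, other tranquilizers, and sedative/hypnotics" and separately says that opioids should be avoided. The documents do not support that. The protocol does not call its list CNS depressants, the SAP does not say that its filter mirrors the list, and opioids are not in that bullet. Adding phenothiazines, general anesthetics or opioids would be a preference.

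Nor does the announcement of three criteria show that a third has been lost. SAP 9.3 goes on to name two sources for these medications, which matches the two criteria given. It is a slip of wording.

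**Conclusion.** The concern holds in a limited form. The medication filter is likely to miss barbiturates recorded as concomitant medications, in the phenobarbital row and in the any-depressant line from concomitant medications of Table 14.1.5.4. The benzodiazepine derivatives row may be mislabelled, because it absorbs a class with a broader name.

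The first statement assumes that CMCLAS holds class names, as SAP 9.3 defines it, and that barbiturates do not sit in one of the other four classes. The second rests on the class name alone.

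The total size cannot be computed; the firm figure is about 0.33 percentage points per affected subject at about 300 subjects.

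A reader might conclude that the counts are wrong in both directions. That is not established. Over-counting of benzodiazepine users would require the contents of the diazepines class, and moving that class to another row would leave the any-depressant line unchanged because the class stays in Criterion 1. Nor are these tables the only record of such use. The matter is a worthwhile correction to a descriptive summary and touches no hypothesis test.

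**What to change.** In SAP 9.3:

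1. Replace `PHENOBARBITAL`, in Criterion 1 and in the category rule, with the barbiturate class value or values that exist in CMCLAS, or match barbiturates on preferred drug name.
2. Report the diazepines class on its own row. It can remain in Criterion 1.
3. Editorial: change the three criteria announced to two.

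The cost is a wording change, a code-list edit and one extra table row. No new data are needed, and no other analysis is affected.
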